12.3.4 Visit 8 (week 12)

The following tasks will be carried out in the consultation during this visit:

- Review the criteria for entry in the maintenance phase.
- Blood pregnancy test (only in women of childbearing potential)
- Samples for full local laboratory test, consisting of:
 - Complete hemogram with reticulocyte and platelet count.
 - Hepatogram,

- Glycemia, lipid profile (HDL, LDL and triglycerides)
- Ionogram, calcium, phosphorus, urea and creatinine,
- Serum iron, transferrin, transferrin saturation, and ferritin
- Serum sample for antibodies and hepcidin dosage (the sample will be collected and stored for further analysis)
- Pulse, will be measured after the patient has been at rest during 5 minutes.
- Blood pressure: 3 measurements separated by 5 minutes each will be taken, for which the patient should be at rest and sitting. The first measurement will be discarded and the values obtained at the second and third measurements will be averaged, a mean value that will be recorded in the medical history and in the case report form (CRF).
- The study medication will be counted and dispensed, and patients will be given a card to record the application of the doses.
- Subcutaneous administration of HEMAX® PFS or EPREX/ ERYPO® will be performed.
- The prescribed doses of HEMAX® PFS or EPREX/ ERYPO® will be recorded, controlling the returned empty boxes and the dose recording cards.
- Adverse events will be recorded and entered in the medical history and in the CRF.
- The patient will be scheduled for the next study visit.

12.3.5 Visits 9 and 10 (weeks 16 and 20 respectively)

The visits will be scheduled four weeks after the previous visit with a window of ± 1 week from the respective date.

The following tasks will be carried out in consultation during these visits:

- Blood pregnancy test (only in women of childbearing potential)
- Pulse, will be measured after the patient has been at rest during 5 minutes.
- Blood pressure: 3 measurements separated by 5 minutes each will be taken, for which the patient should be at rest and sitting. The first measurement will be discarded and the values obtained at the second and third measurements will be averaged, a mean value that will be recorded in the medical history and in the case report form (CRF).
- Complete hemogram. The result of the local hemoglobin test must be within the same day or before so as to be able to adjust the study medication dose, if required.
- The study medication will be counted and dispensed, and patients will be given a card to record the application of the doses.
- Subcutaneous administration of HEMAX PFS or EPREX/ ERYPO® will be performed.

- The prescribed doses of HEMAX PFS or EPREX/ ERYPO® will be recorded, controlling the returned empty boxes and the dose recording cards.
- Adverse events will be recorded and entered in the medical history and in the CRF.
- The patient will be scheduled for the next study visit.

12.3.6 Visit 11 (week 24) or end - of - study visit

This visit will be scheduled four weeks after the previous visit with a window of ± 1 week from the respective date.

The following tasks will be carried out in the consultation during this visit:

- Blood pregnancy test (only in women of childbearing potential)
- Samples for full local laboratory test, consisting of:
 - Complete hemogram with reticulocyte and platelet count.
 - Hepatogram,
 - Glycemia, lipid profile (HDL, LDL and triglycerides)
 - Ionogram, calcium, phosphorus, urea and creatinine,
 - Serum iron, transferrin, transferrin saturation, and ferritin
 - Serum sample for antibodies and hepcidin dosage (the sample will be collected and stored for further analysis)
- Pulse, will be measured after the patient has been at rest during 5 minutes.
- Blood pressure: 3 measurements separated by 5 minutes each will be taken, for which the patient should be at rest and sitting. The first measurement will be discarded and the values obtained at the second and third measurements will be averaged, a mean value that will be recorded in the medical history and in the case report form (CRF).
- The prescribed doses of HEMAX PFS or EPREX/ ERYPO® will be recorded, controlling the returned empty boxes and the dose recording cards.
- Medication accounting will be performed
- Adverse events will be recorded and entered in the medical history and in the CRF.

12.3.7 Unscheduled visit

An unscheduled visit can be made at any time during the study, if the patient requests so or in the event that the investigator deems it necessary. The date and the reason for the unscheduled visit will be

recorded in the medical history. The following items will be recorded in the CRF:

- adverse events,
- changes in medication and concomitant medications.

All the other activities and evaluations are optional according to the investigator's judgment.

13 INVESTIGATIONAL PRODUCT/ STUDY DRUGS

13.1 METHOD OF PATIENT ALLOCATION TO A TREATMENT GROUP

All patients will be randomized by an electronic randomization system, stratified by sex and in blocks by site.

13.2 BLINDING

This is not applicable as this is an open-label study.

13.3 CODE UNBLINDING DUE TO EMERGENCY

This is not applicable as this is an open-label study.

13.4 POST STUDY ACCESS

If at the end of the study, the patient has the indication to continue with the treatment with epoetin and his current healthcare provider does not provide it, BIOSIDUS will provide the patient with epoetin (Hemax PFS® or Hemax®) free of charge until it becomes available through patient's healthcare provider.

13.5 INVESTIGATIONAL PRODUCT/ STUDY DRUGS DESCRIPTION

HEMAX PFS will be used in prefilled syringe in 1000 IU/ 0,5ml, 2000 IU/0,5ml, 3000 IU/0,3ml and 4000 UI/0,4ml presentations.

The sponsor Biosidus Argentina SA, is responsible for the manufacture of HEMAX PFS in accordance with the Good Manufacturing Practice (GMP) guidelines.

The solution for injection should be kept in the refrigerator, at a temperature between 2°C and 8°C.

EPREX/ ERYPO® injectable in prefilled syringe in 1000 IU/0,5ml, 2000 IU/0,5ml, 3000 IU/0,3ml and 4000 IU/0,4ml.presentations will be used as reference.

The manufacturer Janssen Cilag, Germany, is responsible for the manufacture of Eprex/ ERYPO® in accordance with the Good Manufacturing Practice (GMP) guidelines.

The solution for injection should be kept in the refrigerator, at a temperature between 2°C and 8°C. The study drugs will be dispensed according to the following diagram:

Medication	Presentation to be dispensed	Titration phase (week 0 to week 12)	Maintenance phase (week 12 to week 24)
HEMAX®	Injectable, 2000 IU/ 0.5ml and 4000 IU/ 0.4 ml in a sufficient amount depending on the dose to be administered.	The initial dose will be 29IU/ kg estimated for an average weight of 70 Kg, what equals to 2000IU twice a week. Dose adjustments will be in aliquots of 25% of the dose that the patient was receiving It is estimated that the mean weekly dose will be 5000 IU ± 2500 IU/ ml. Given that visits are every 2 weeks and that in each visit the medication will be administered at the site, only the necessary amount for the biweekly dose (3 doses) will be dispensed which will not be administered at the site.	The weekly dose will be estimated based on the total dose that the patient was receiving until week 12. That is to say, a patient that was receiving 2000IU/ 0.05 ml twice a week will start to receive 4000IU/ 0.4ml on a weekly basis Dose adjustments will be in aliquots of 25% of the dose that the patient was receiving It is estimated that the mean weekly dose will be similar to the weekly dose administered twice a week. Given that visits are every 4 weeks and that in each visit the medication will be administered at the site, only the necessary amount for the weekly dose (3 doses) will be dispensed which will not be administered at the

site.

The drug supplies should be stored in a safe place, in a refrigerator with limited access and in appropriate conditions, with temperatures between 2° C and 8° C. Only authorized staff will have access to the study drug at study sites.

Patients will also be administered supplements of:

- **Ferrous sulphate**, tablets of 200 mg that will be presented in the packaging with the approved package insert for use in our country and which will be administered according to the criterion of the investigator in order to maintain the transferrin saturation above 20% during the study.

13.6 ACCOUNTABILITY AND COMPLIANCE

The patient will return all the study drugs both used and not used. The site staff will only record in the source document and in patient's individual accountability record the patient number and the number of study drug packages returned.

During the study, the monitor will continuously review all the study drugs (bottles used and unused) and the corresponding accountability forms. Also the card where the patient will record the administered medication doses will be reviewed at each visit. The accountability records of the study drugs will be filed at all times at the sites. At the end of the study, a final accountability will be performed and all the remaining drugs will be removed for destruction according to the current regulations.

14 EVALUATION METHODS

14.1 METHODS OF EFFICACY EVALUATION

The following parameters will be evaluated for treatment efficacy, according to the objectives defined by the protocol at each visit:

- Levels of hemoglobin and its variation at each visit, with intragroup and intergroup comparison
- Percentage of responder patients, defined as the increase of Hb ≥ 1 g/ dl without transfusion requirement.
- Number and percentage of patients that require at least one transfusion.

14.2 SAFETY PARAMETERS

14.2.1 Adverse events

Adverse events will be recorded from the moment in which the patient signs the informed consent and will be recorded throughout the study. These should be reviewed and updated at each subsequent visit and during any telephone contact with the patient.

14.2.2 Vital signs

Pulse and blood pressure measurements will be made at each visit.

14.2.3 Medical history

At baseline visit (week - 1), a medical history will be made and all clinically relevant data will be recorded in the source documents of the patient and in the individual case record form (ICRF). The medical history will include the registration of the concomitant medication which will be recorded in the source documents of the patient and in the individual case record form (ICRF), which will be updated as changes occur at each visit.

14.2.4 Physical exam

At baseline visit (week - 1), a physical examination will be performed and all clinically relevant data will be recorded in the source documents of the patient and in the individual case record form (ICRF).

14.2.5 Physical Examination

A brief physical examination will be performed at the baseline visit (week -1) and all clinically relevant data should be recorded in the patient's source documents and on the individual case record form (ICRF).

14.2.6 Electrocardiogram

At baseline visit (week - 1) an electrocardiogram will be performed and all clinically relevant data will be recorded in the source documents of the patient and in the individual case record form (ICRF).

14.2.7 Full laboratory tests

A full laboratory test will be performed at the baseline visit (week - 1) and at the week 12 and week 24 visits or at study completion visit and all clinically relevant data will be recorded in the source documents of the patient and in the individual case record form (ICRF). Samples for full local laboratory test will consist of:

- Complete hemogram with reticulocyte (through flow cytometry or hematologic counter) and platelet count.
- Hepatogram,
- Glycemia, lipid profile (HDL, LDL and triglycerides)

- Ionogram, calcium, phosphorus, urea and creatinine,
- Serum iron, transferrin, transferrin saturation, and ferritin
- Beta subunit of chorionic gonadotropin only in women of childbearing potential
- Serum/ plasma sample for antibodies and hepcidin dosage (the sample will be collected and stored frozen at - 20° C for further analysis)

14.2.8 Complete hemogram

A complete hemogram will be performed at week 4, 6, 8, 10, 16 and 20 visits and all clinically relevant data will be recorded in the source documents of the patient and in the individual case record form (ICRF). The result of the local hemoglobin test must be within the same day or before so as to be able to adjust the study medication dose, if required.

14.2.9 Blood pregnancy test

A blood pregnancy test will be performed only in women of childbearing potential at week -1, 2, 4, 6, 8, 10, 12, 16, 20 and 24 visits. All clinically relevant data will be recorded in the patient's source documents and in the individual case record form (ICRF).

15 SAFETY AND ADVERSE EVENTS

Adverse events

An adverse event (EA) is defined as any undesirable medical condition, in a patient in a clinical trial to whom a medical product was administered, without necessarily having to present any causal relationship with the treatment.

In the study, any event that occurs once the patient included in the clinical trial has signed the study informed consent and has received at least one dose of the study medication should be recorded and reported as an AE.

An adverse event can therefore be any unfavorable and unintended sign (including abnormal laboratory findings), symptom, or disease temporally associated with the use of a medicinal product under investigation, whether or not considered related to that medical product.

For adverse events with a causal relationship to the investigational product, the investigator will be required to follow up until the event or its sequelae resolve or stabilize to a level acceptable to the investigator.

A new problem or the worsening of a preexisting one will be considered as an AE. A stable chronic problem, such as arthritis that exists before the start of the study and that does not worsen during the same will not be considered an AE.

An abnormal result from a diagnostic procedure, including abnormal laboratory findings, will be considered as an AE when:

- It results in the withdrawal of the patient by the investigator
- It is associated with a serious adverse event (SAE)

- It is associated with clinical signs or symptoms
- The physician considers it clinically relevant

The investigator will establish, according to his own criterion, if the AEs do or do not have a **causal relationship with the study drug**, in accordance with the following assessment of causality of adverse reactions possibly related to the study drug.

The following 4 - point scale will be used to establish the **causality relationship**:

- **Unrelated:** Events that do not follow a reasonable temporal sequence from the administration of the study drug or that can be reasonably explained by the base disease, complications, concomitant medication or treatment or environmental factors.
- **Possible:** Event that follows a reasonable temporal sequence from the administration of the study drug (including study medication suspension or dose reduction) with reasonable possibility that the adverse event has been caused by the study medication but also may have been caused by the base disease, complications, concomitant medication or treatment or environmental factors.
- **Probable:** Event that presents a clear temporal relationship, with improvement upon study medication suspension or dose reduction and when the causality due to other factors such as the base disease, complications, concomitant medication or treatment or environmental factors can be reasonably excluded.
- **Defined:** Event with clear temporal relationship, with improvement upon study medication suspension or dose reduction and recurrence upon treatment reinitiation.

Depending on its **intensity or degree of severity**, the AEs are classified as follows:

- **Mild:** It does not significantly interfere with the daily activities of the subject, disappears without leaving any residual effect.
- **Moderate:** It significantly interferes with the study and/ or with the daily activities of the subject, and may or may not require treatment.
- **Severe:** It significantly interferes with the study and/ or with the daily activities of the subject, it requires treatment or suspension of the study medication and is considered as unacceptable at the physician or the patient's criterion and may require withdrawal from the study.

A **serious adverse event (SAE)** is defined as an AE that results in any of the following results:

- Death;
- Life threat;
- Requires or prolongs hospitalization;

- Causes persistent or significant inability / disability;
- It is a congenital anomaly or birth defect;
- It is a major medical event that requires a medical intervention to prevent the results mentioned in the previous points.

Important medical events are those that may not be immediately life threatening but that may endanger the patient and require an intervention to prevent one of the other serious results listed above. Examples would be an intensive treatment in the emergency room or at home due to an allergic bronchospasm, blood dyscrasia or seizures that do not result in hospitalization but that, if not treated, would have threatened the life or resulted in death; an adverse event of this type, resolved, will be considered as serious according to this criterion.

The **hospital admission** or the prolongation of an existing hospitalization means that the patient's admission to the hospital for more than 24 hours and/ or the prolongation of the hospitalization was necessary for the treatment of an AE or that it occurred as a result of the event. It does not refer to a preplanned elective hospital admission for the treatment of a preexisting disorder that has not significantly worsened, nor to diagnostic procedures.

The term "**life - threatening**" in the definition of "serious" refers to an event in which the patient ran a risk of death at the time of the event; it does not refer to an event which hypothetically could have caused the death had it been more severe.

Any new SAE that occurs after the study period and is considered related (reasonable possibility) with the study drug or with the participation in the study, must be registered and reported immediately. The study period for SAE reporting is defined as the period from the time of the signing of an informed consent until the end of the follow - up period (30 days after the last dose).

SAE reporting: To comply with the regulatory requirements, any serious adverse event, considered related or not with the study drug, should be brought to the attention of the sponsor or designee as soon as the investigator or the coordinator becomes aware of the same. The SAE form must be completed and sent without delay, even if not all information was available at the time of the initial contact.

The SAE must be reported to the sponsor or designee within 24 hours after becoming aware of the event.

The SAEs occurred in Argentina will be sent directly or through the person responsible for monitoring the clinical study to:

Biosidus, Departamento de Investigación Clínica

[name]

[contact]

[contact]

Any relevant additional follow - up information on a SAE that was not possible to provide in the initial report will be sent by the site within 24 hours from the moment on which the new information is obtained.

The *Unidad de Seguridad de Medicamentos* of Biosidus S.A. will make a pharmacovigilance report for those cases that require so, in order to notify to the appropriate authorities, in accordance with the current regulations.

Pregnancy reports: Pregnancy reports should be sent to the *Unidad de Seguridad de Medicamentos* of Biosidus S.A. so as to be included in the safety database. This also includes the normal pregnancies without AEs.

A pregnancy follow - up must be made in order to determine pregnancy results, including spontaneous or voluntary interruption, the birth details, the presence or absence of any birth defect, congenital anomalies or complications in the mother or in the newborn. The pregnancy follow - up report should be registered in the specific ICRF, provided by the sponsor.

The procedure for pregnancy reporting must be the same as the procedure for SAE reporting.

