9.1 Adverse Events

As safety objective, the incidence of adverse events and adverse reactions will be evaluated after 12 and 24 weeks of treatment, comparing patients treated with HEMAX PFS versus those treated with EPREX/ ERYPO®.

An AE shall be considered as treatment - emergent adverse event (TEAE), if it presents after the first dose administered of the investigational product or if, preexistent prior to the administration of the first dose, it worsens after the administration of the same.

All TEAEs will be presented summarized through the use of Tables, for each organ class and preferred term to denominate them. The Tables will present the number of patients for which events occurred, and the incidence rate, expressed as a percentage calculated on the number of patients from the entire population included in the safety FAS.

The TEAEs will be presented by causality (relationship with the study drug), intensity (mild, moderate, severe). Treatment - emergent events that are serious and that lead to treatment discontinuation will also be summarized using the preferred term and the class organ system involved.

In addition, and with focus on safety, the following will be discussed:

- Incidence of thromboembolic events (myocardial infarction, cerebrovascular accident, deep vein thrombosis and other thromboembolic events).
- Incidence of hypertension as TEAE.
- Blood pressure values at each visit.
- Complete baseline laboratory data and at week 12 and 24 visits,
- Antibody dosages, baseline and at weeks 12 and 24.

For safety analysis, descriptive statistics will be performed mainly to evaluate the incidence of adverse events and adverse reactions after 12 and 24 weeks of treatment.

When calculating the incidence of adverse events, or any sub-classification (e.g. by treatment) each subject will be counted all the times a repetitions of adverse events will be occurred and the denominator will be the total population size.

All the adverse events occurred during the study will be listed according to treatment group and severity. The frequency of adverse events by system and treatment group, expressed as amount of events/number of affected patients and the relationship with study drug will be summarized.

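### The adverse event intensity scale has no grade for a persistent event that interferes with neither the study nor daily activities, and its grades overlap without a tie-break rule

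*Protocol*

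**What the plan says.** Protocol section 15 defines three grades of intensity:

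- A mild event has no significant effect on daily life and, as a second condition, "disappears without leaving any residual effect". Effect on the study is not mentioned.
- The moderate grade is worded as "It significantly interferes with the study and/ or with the daily activities of the subject, and may or may not require treatment".
- For severe, the interference condition is the same as for moderate, and the definition adds "it requires treatment or suspension of the study medication and is considered as unacceptable" in the opinion of the physician or the patient. Withdrawal is possible but not required.

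No rule covers an event that fits none of these or more than one.

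The grades feed planned output. SAP 9.1, repeating Protocol 16.6, states: "The TEAEs will be presented by causality (relationship with the study drug), intensity (mild, moderate, severe". SAP 9.1 adds: "All the adverse events occurred during the study will be listed according to treatment group and severity". The SAP does not redefine the grades.

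Hypertension is one of the safety topics singled out in both documents ("Incidence of hypertension as TEAE"). A finding without symptoms can be an adverse event: among the conditions in Protocol section 15 under which an abnormal test result counts is "The physician considers it clinically relevant".

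SAP 9.1 also has two counting rules. One reports the number of patients with events as a percentage of patients. The other counts a subject again each time an event recurs, over the same patient denominator.

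**The concern.** A grading scale should give each event exactly one grade. This one mixes three ideas: how much the event interferes, how it ends, and what treatment it needs.

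Because mild includes a condition on outcome, and the higher grades require interference, an event that lingers without interfering has nowhere to go. Such events are foreseeable here. Blood pressure is measured at every visit, so asymptomatic rises will be seen. The protocol also accepts that related events may stabilise rather than resolve. An event still open at the final visit has not met the mild definition either.

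At stake is the consistency of the intensity table between sites and arms. Faced with the same event, one investigator might depart from the wording and choose mild, another might choose moderate, and a third might leave the field blank.

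**Working it through.** The plan states no figure to reproduce, and no power, margin or event-rate input is involved. The check is one of logic: do the three definitions cover every case, and cover it once?

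**Inputs.** Five yes/no attributes appear in the definitions in Protocol section 15:

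- S: significant interference with the study
- D: significant interference with daily activities
- R: resolves with no residual effect
- T: needs treatment or suspension of study drug
- U: judged unacceptable

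**Definitions**, treating the optional clauses as non-binding:

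- Mild = (not D) and R
- Moderate = S or D
- Severe = (S or D) and T and U

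There are 2^5 = 32 combinations.

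**Gap.** Failing moderate means S = 0 and D = 0. Failing mild as well then means R = 0. T and U are free, so 2 × 2 = 4 combinations have no grade. All four are persistent and interfere with neither the study nor daily life.

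**Overlaps.** Three of the four (S, D) pairs meet moderate, giving 3 × 8 = 24 combinations. Severe fixes T = U = 1 and leaves R free, giving 3 × 2 = 6, all inside the 24. Mild fixes D = 0 and R = 1, giving 8. Of those, the 4 with S = 1 also meet moderate, and 1 of these 4 also meets severe.

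| Grades met | Combinations |
|---|---|
| None | 4 |
| Mild only | 4 |
| Moderate only | 15 |
| Moderate and severe | 5 |
| Mild and moderate | 3 |
| All three | 1 |
| Total | 32 |

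Exactly one grade: 4 + 15 = 19. More than one: 5 + 3 + 1 = 9. None: 4.

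**How far the gap reaches.** Take the 8 combinations that persist and leave daily activities unaffected (D = 0, R = 0). The 4 with S = 0 have no grade. The 4 with S = 1 can be graded: 3 as moderate only, 1 as moderate and severe. Whether a given case of persistent hypertension is ungraded therefore turns on whether it interferes with the study, a term the documents do not define.

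**Check of the repair.** Let mild mean neither S nor D, keep the other two definitions, and assign the highest grade met. Mild then has 8 combinations, severe 6, and moderate 24 − 6 = 18. The total is 8 + 18 + 6 = 32, each with one grade.

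**Scale of one misgraded patient.** SAP section 5 reports 23 and 20 patients. If all were dosed, moving one patient between grades shifts that arm's percentage by 1/23 = 4.3 points or 1/20 = 5.0 points.

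**The case against.** The strongest reply is that the mild definition need not be read as two binding conditions. Its second clause follows a comma, with no conjunction, and may only describe a typical mild event. Untranslated Spanish elsewhere (Protocol 11.2, SAP 6.3) suggests the wording passed through translation. Many investigators would simply record such an event as mild. This is plausible and is one reason the point is minor. But the text does not say so, and no other section closes the gap.

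The second reply is that severe sitting inside moderate is normal for an ordered scale, and that assigning the highest grade met is the natural reading. That largely stands: one sentence would settle both overlaps. It does nothing for the gap.

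The case report form is not among the documents, so outcome may already have its own field.

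A reader might infer four stronger things that the documents do not support:

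- *That persistent asymptomatic hypertension cannot be graded at all.* It can be moderate if it interferes with the study.
- *That the moderate/severe overlap causes the hypertension problem.* The overlap concerns only events that do interfere.
- *That the primary safety comparison is compromised.* The primary safety objective and the chi-square test in Protocol 16.6 concern incidence. Intensity is presented descriptively, and the hypertension items use no grade.
- *That a number of affected patients can be given.* The documents contain no rate for such events.

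The unblinded nature of the moderate/severe judgement is a general feature of an open-label trial. Rewording the grades would not remove it.

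**Conclusion.** The point holds as a minor defect of a stated rule. Read literally, the scale is neither exhaustive nor mutually exclusive. The number of patients affected cannot be derived, because no event rate is given and study interference is undefined.

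The consequence is missing or inconsistent entries in the intensity table and the severity listing. With arms of about 20 patients, a few such entries would be visible. Incidence of adverse events and reactions, the separately defined serious events, and the efficacy analyses do not use the scale.

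The conclusion assumes that the resolution clause in mild is a condition, that the optional clauses in moderate and severe are not, and that no unseen instruction to sites fills the gap.

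**What to change.** In Protocol section 15:

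- Remove the resolution clause from mild, and define mild as no significant interference with either the study or daily activities.
- State that the highest applicable grade is assigned.
- Record outcome and residual effect separately from intensity.

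SAP section 5 reports that enrolment has closed and that the last patient reached the primary evaluation in March 2021, so new wording will not alter grades already given. For data in hand, SAP 9.1 should state that:

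- grades assigned by investigators are kept;
- an ungraded treatment-emergent event that interferes with neither the study nor daily activities is tabulated as mild, whatever its duration;
- each patient is counted once, at worst grade, in the incidence-by-intensity table, replacing the rule that counts a subject at every recurrence, with event counts shown separately.

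Keeping investigator grades matters. A blanket rule turning every event without effect on daily life into mild could override judgements already made, and would reclassify events that disturb only the study.

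The cost is a few sentences and possibly a data query for ungraded events.
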